### **Recruitment and Training of Peer Coaches**

Recruitment: We have three primary sources for recruiting peer coaches: 1) Veterans who served as peer coaches in IMPPRESS (7 out of 9 expressed interest in serving as a coach again); 2) Veterans who completed the intervention arm of one of our previous chronic pain studies involving pain self-management instruction (ESCAPE, PI: [name]; CAMEO, PI: [name]; SCOPE, PI: [name]). In these studies completers were asked for permission to be contacted for future studies. We successfully recruited 10 peer coaches for IMPPRESS in one month using this approach. From these two completed and one ongoing study we have a pool of approximately 250 potential peer coaches. 3) Veterans with chronic pain (see ICD-9 codes in Section D2c) who are recommended by their PCPs. Although we did not need this strategy in IMPPRESS because of successful recruitment of participants from prior studies, one of our co-investigators, [name], has successfully used this method for peer studies of Veterans with diabetes.

Manual: Each peer coach will be given a manual to refer to and serve as a guide during the intervention. The Peer Coach Manual consists of two parts: 1) Self-Management Knowledge (this portion is identical to the Veteran manual), and 2) How to be a Peer Coach. See Table 1. This manual was developed and refined in IMPPRESS, drawing on the study manual from [name] ESCAPE trial (Part 1), and on the Peer Specialist Manual used by VHA's Office of Mental Health Services (Part 2, shared by [name], Director of VA Peer Support Services, see letter of support). In addition, during IMPPRESS, our study psychologist, [name], developed a section on motivational strategies, grounded in the motivational interviewing literature. The peer coach manual is in Appendix 1.

Training: Three to 4 coach training sessions will be scheduled as coaches are recruited. Once 10 coaches are recruited, a training session will be scheduled, and coaches will be assigned Veterans. This process will continue until all peer coaches are recruited, trained, and matched with Veterans.

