### **Data Analysis**

**Sample Size Determination.** Our sample size is calculated based on estimated intervention effect on the primary outcome, the Brief Pain Inventory (BPI) total score, a continuous measure. Effect sizes for the BPI in past studies by our team have ranged from .4 to .6. Because this is our first large-scale trial with peer coaches, we will conservatively power the study based on an effect size of .4. To test for a significant difference between the BPI change from baseline to the primary 6-month endpoint between the treatment and control arm, will use a linear mixed model. With a two-sided test and a Type I error of .05, we will have 80% power to detect a .4 effect size with 102 Veterans and 34 peer coaches in the treatment group and 80 Veterans in the control arm, assuming equal variance across the two treatment arms, 3 Veterans per peer coach, and an intra-class correlation (ICC) in the treatment group of .3, which was observed in IMPRESS. (A smaller N is required in the control group because they are not nested within peer coaches.) In our prior chronic pain trials at RVAMC, retention rates were >90%. With a conservative 15% attrition rate, we will need 120 (102/.85) Veterans in the treatment arm, 40

coaches, and 95 (80/.85) Veterans in the control arm, for a total N = 215 Veterans and N = 40 coaches. We plan an intent-to-treat analysis approach.

Consistent with previous studies at RVAMC, the sample will include at least 15% minorities, reflecting the demographics of our medical center. In our SCAMP study, Blacks comprised 16% of the Veteran sample and 13% in ESCAPE. We do not plan to over-sample minorities or power sufficiently to explore racial differences in treatment response. The racial/ethnic composition of RVAMC and participating CBOCs makes exploring racial differences in treatment response impractical unless we employed special efforts to recruit minorities other than Blacks.

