**Data Analysis for Aim 1.** We will summarize total BPI score at each time point (baseline, 6, and 9 months) for both study arms. To compare the primary outcome of total BPI score at each time point relative to baseline between two treatment arms, we will use a linear mixed-effects model fit to all time points. This model will allow us to compare the change in BPI from baseline to 6 months (primary endpoint) between treatment groups, while accounting for the correlation of measurements from the same Veteran/peer coach and adjusting for confounding factors. Fixed effects in the model will include an indicator for treatment group, time (baseline, 6, and 9 months.), treatment group by time interaction, and covariates found to differ significantly between treatment and control arm. Random effects will include a random patient-specific intercept and a random effect for peer coach within the treatment arm only. Additionally, the variance may be allowed to differ between treatment and control arms. Because this is a randomized trial design we do not expect covariates to significantly differ between the two groups. However, if there are statistically significant differences, these covariates will be included in the model. The linear mixed model for subject  $i$  in therapy group  $j$  at time  $k$  is

$$y_{ijk} = \beta_{10} + b_i + x_{ijk}'\beta + \gamma_{11}t_{ij1} + \gamma_{12}t_{ij2} + (1 - I_{ijk})r_{ijk} + (\beta_{20} + b_i + \gamma_{21}t_{ij1} + \gamma_{22}t_{ij2} + u_j + e_{ijk})I_{ijk}$$

where  $I_{ijk}$  is an indicator if patient is assigned to the treatment group,  $x_{ijk}$  is a vector of fixed covariates,  $t_{ij1}$  is an indicator for the 6-month time point,  $t_{ij2}$  is the indicator for the 9-month time point,  $b_i \sim N(0, \varepsilon^2)$  are patient-specific intercepts,  $\mu_j \sim N(0, \sigma_j^2)$  is the random effect due to peer coach  $j$ ,  $e_{ijk} \sim N(0, \sigma_T^2)$  and  $r_{ijk} \sim N(0, \sigma_C^2)$  are the residual errors for each treatment group. All analyses will include checking of assumptions and model fit. Our statistical model, which accounts for nesting of Veterans within peer coaches, will allow us to calculate the intra-class

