correlation (ICC) in the treatment group to evaluate whether there are substantial variations among peer coaches. In secondary analyses, we will also look at the BPI subscales of pain intensity and interference separately, using a similar mixed-model approach and adjusting for multiple comparisons using the Šidák method to maintain the overall confidence at 95% and to adjust for multiple comparisons. To determine if fidelity moderates patient outcomes, we will include the peer coach fidelity score by treatment group interaction and the interaction (fidelity score by time by treatment group) for the 9-month time point in the model above.

**Data Analysis for Aim 2.** Secondary measures of self-efficacy, pain coping, patient activation, social support, and health-related quality of life are continuous measures; thus the linear mixed-effects model described above will also be appropriate to analyze these measures. If a linear mixed model does not seem appropriate for a given scale, then a generalized linear mixed-effects model will be used. Since there will be a number of secondary outcomes, we will use the Šidák method. Health care utilization (number of ED visits, hospitalizations, outpatient visits, telephone visits, and analgesic prescriptions, including opioids) over the 9-month intervention will be analyzed using a generalized linear mixed model, assuming the counts follow a Poisson or negative binomial distribution. Explanatory variables in the model will include treatment indicator and, if necessary, a random effect for peer coach within the treatment group only. Covariates that significantly differ between groups will be included. If counts include a high proportion of zeros, a zero-inflated count model may be required.

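### The fidelity analysis has a three-way term for 9 months but none for 6 months, so coach fidelity cannot affect the primary baseline-to-6-month change in the model as written

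*Combined protocol and SAP*

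**What the plan says.** Data Analysis for Aim 1 describes one model for BPI total: "we will use a linear mixed-effects model fit to all time points". Baseline is an outcome row, not a covariate. The equation has separate indicators for 6 and 9 months, each with its own treatment-specific coefficient, and baseline is the reference level. The model's stated purpose is to "compare the change in BPI from baseline to 6 months (primary endpoint) between treatment groups".

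The fidelity analysis extends that model. Its aim is given as "To determine if fidelity moderates patient outcomes". One sentence lists the terms to be added. The first is a two-way product of the coach's score and study arm, with no time index. The second is worded as follows: "the interaction (fidelity score by time by treatment group) for the 9-month time point in the model above". No three-way term for 6 months is named there or elsewhere in the document.

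**The concern.** In the main equation treatment enters three times: as an arm difference at baseline, as a 6-month change and as a 9-month change. The fidelity extension has counterparts for the first and third but not the second, which is the one that carries the primary endpoint.

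The plan therefore asks whether fidelity moderates outcome but yields no estimate at its own primary time point. A real fidelity effect on 6-month change is pushed partly into a baseline association and partly into the 9-month term. It could be reported as absent, or as reversing at 9 months. This matters in a trial that rates coach fidelity by observation and also studies implementation.

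**Working it through.** **Inputs from the document.** Outcome rows at baseline, 6 and 9 months, with baseline as reference, and two added fidelity terms (Data Analysis for Aim 1). "102 Veterans and 34 peer coaches in the treatment group", 80 controls, 3 Veterans per coach, ICC .3, two-sided .05 (Sample Size Determination). The document gives no figure for the fidelity analysis, so there is none to reproduce.

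**Assumptions.** Fidelity F is a coach-level score, standardised, and 0 in controls. Total variance is 1 and coach variance 0.3. The remaining 0.7 is split patient/residual as 0.2/0.5, 0.35/0.35 or 0.5/0.2. Variances are treated as known in the power figures.

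**Step 1: slopes implied by the written terms.** Let d1 be the coefficient of F × treatment and d2 that of F × 9 months × treatment.

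| Visit | Treated-arm fidelity slope |
|---|---|
| Baseline | d1 |
| 6 months | d1 |
| 9 months | d1 + d2 |

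- Fidelity effect on baseline-to-6-month change: d1 − d1 = 0.
- Fidelity effect on baseline-to-9-month change: (d1 + d2) − d1 = d2.

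The zero is algebra and needs no assumption about variances or slopes.

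**Step 2: what d1 and d2 estimate.** Let the true slopes be s0, s6 and s9. With complete data the random effects give equal correlation between visits, so the fit averages the two visits forced to share a slope:

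- d1 → (s0 + s6)/2
- d2 → s9 − (s0 + s6)/2

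The target at 9 months is s9 − s0, so d2 misses it by (s6 − s0)/2.

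**Step 3: numbers, with s0 = 0 and s6 = −0.30 (assumed).** In every row d1 = (0 − 0.30)/2 = −0.15 and the implied 6-month effect is 0.

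| True s9 | d2 = s9 + 0.15 | True effect on 9-month change |
|---|---|---|
| −0.30 | −0.15 | −0.30 |
| −0.15 | 0.00 | −0.15 |
| 0 | +0.15 | 0 |

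Exact generalised least squares gave these values. A separate simulation (40 coaches × 3 Veterans, 95 controls) gave d2 = −0.15 for the first row and +0.16 for the third. With 15% missing at random, d2 moved by less than 0.01.

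**Step 4: power.** For coach means over 3 Veterans, put A = 0.3 + patient variance/3 (shared across visits) and B = residual variance/3 (visit-specific).

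- *As written.* The baseline/6-month slope and the 9-month slope have covariance matrix [[A + B/2, A], [A, A + B]]/34. For the 0.2/0.5 split, A = 0.367 and B = 0.167. With fitted slopes (−0.15, −0.30) the noncentrality is 34 × 0.0195/0.1056 = 6.28, which on 2 df gives about 61% joint power.
- *With the 6-month term.* The 6- and 9-month terms have covariance matrix B × [[2, 1], [1, 2]]/34. With slopes (−0.30, −0.30) the noncentrality is 34 × 0.06/0.167 = 12.24, giving 89%.

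Over the three splits:

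| True s9 | Joint power, two written terms | Joint power, 6- and 9-month terms in the corrected model |
|---|---|---|
| −0.30 | 61–83% | 89% to >99% |
| −0.15 | 18–21% | 78–99% |

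The standard error of the added 6-month term is √(2 × residual variance/102): √(1.0/102) = 0.099 down to √(0.4/102) = 0.063. Its own power at −0.30 is 86% to >99%. The written model is full rank (8 of 8), so software would fit it without warning. The corrected model is also full rank (9 of 9) and recovers every true slope.

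**The case against.** The strongest reply is that fidelity × treatment was meant to be the 6-month effect, with the three-way term as the additional 9-month effect. Fidelity is rated during the intervention (Optimizing Intervention Fidelity), so no score exists at baseline. If F is coded 0 on baseline rows, the treated slopes become 0, d1 and d1 + d2. The true values are then recovered exactly: d1 = −0.30, and d2 = 0, +0.15 and +0.30 in the three cases. That reading is possible, but the text does not give it. The score is the peer coach's, the treatment indicator is defined only by assignment, and nothing restricts the two-way term to post-baseline rows or fixes the baseline slope at zero. An analyst following the sentence would fit the model in Step 1.

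Second, the sizes are hypothetical, and that stands. The plan gives no fidelity slope, no fidelity SD and no within-patient correlation. The corrected-model power also relies on a coach effect constant over time, as in the plan's equation, which cancels from change. If coaches differed in the change itself with ICC .3 (design effect 1 + 2 × 0.3 = 1.6), the standard error of the 6-month term would be 0.079–0.125 and its power 67–97%. At a slope of −0.15 the original standard errors give 33–67%. In addition, 61–83% joint power in the constant-effect case means the written terms would often detect something there, though not attribute it to the right visit.

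Third, the scope is narrow: one secondary analysis that is not a stated aim. That also stands.

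**Conclusion.** The concern holds. With the stated terms, the fidelity effect on baseline-to-6-month change is zero by construction, and the 9-month term is off by half the difference between the 6-month and baseline slopes. The distortion disappears only if those two slopes are equal, which is what the analysis is meant to test. Under the assumed −0.30 slope at 6 months, the 9-month term is halved, vanishes or takes a spurious positive value, depending on the true 9-month slope.

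The structural result assumes only that a coach's score applies to all of that coach's rows, which is how the sentence reads. The slopes and powers are illustrations. This should be corrected before analysis. The primary treatment comparison, the sample size and trial conduct are not affected.

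**What to change.** Amend the fidelity sentence in Data Analysis for Aim 1 as follows.

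- Add the fidelity × 6-month × treatment term beside the 9-month one, and name it as the main fidelity estimate.
- Keep fidelity × treatment as the baseline slope. The plan says coaches and Veterans will be matched ("until all peer coaches are recruited, trained, and matched with Veterans") but not how, so a baseline association cannot be ruled out.
- State that the fidelity terms are 0 in controls, who have no coach, and that there is no separate fidelity main effect.
- Describe the result as an exploratory, non-randomised association across 34–40 coaches within the treatment arm, since controls carry no information on fidelity.

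Constraining the baseline fidelity slope to zero would also make the two written terms interpretable. It would have to be stated, and it assumes matching is unrelated to baseline pain.

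The cost is one sentence, one more parameter and a more modest claim. No new data are needed.

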### **Data Collection Protocol for Primary and Secondary Measures (Aims 1 and 2)**

Assessments will be given at baseline, 6 and 9 months. Participants (intervention and control) will receive \$30 per assessment. We will administer the same measures to peer coaches and Veterans, because research suggests peer coaches also benefit from peer interventions. Moreover, we want to determine whether the peers experience any negative effects related to their participation.

After obtaining informed consent, a research assistant will administer a baseline assessment to gather socio-demographic data, review the Veteran's history with an emphasis on previous and current pain treatments, and administer measures of primary and secondary outcomes. These assessments will take approximately 30 minutes each.

**Aim 1 (Primary Outcome): To compare 6- and 9-month effects of peer-supported chronic pain self-management versus controls on overall pain.** Overall pain will be measured with the Brief Pain Inventory (BPI) total score. The BPI was developed to assess the severity of pain and the impact of pain on daily functioning, and has been validated in primary care studies. The BPI is the average of two scores: pain intensity and pain interference. The pain intensity score is an average of 4 ratings of 0 (no pain) to 10 (pain as bad as you can imagine) for current, least, worst, and average pain in the past week. The BPI pain interference score averages seven ratings, 0 (does not interfere) to 10 (interferes completely), of interference with general activity, mood, walking ability, normal work, relations with other people, sleep, and enjoyment of life. The BPI total score will be used as the primary outcome measure because BPI total has been shown to be highly responsive to change in clinical trials. The BPI has been shown to have strong internal consistency in its original validation study (Cronbach's  $\alpha = 0.77$ ), the SCAMP study ( $\alpha = .83$ ), and IMPPRESS ( $\alpha = .88$ ); and the BPI assesses the two most important domains—severity and interference—recommended for pain studies.

**Aim 2 (Secondary Outcome Measures): To compare 6- and 9-month effects of peer-supported chronic pain self-management versus controls on self-efficacy, pain coping,**

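### A step-down (Holm-)Šidák test would never be less powerful than the Šidák adjustment named for the BPI subscales and Aim 2, and costs almost nothing to adopt

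*Combined protocol and SAP*

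**What the plan says.** The Combined protocol and SAP names the adjustment twice under Data Analysis.

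- **BPI subscales (end of Data Analysis for Aim 1).** The plan says "we will also look at the BPI subscales of pain intensity and interference separately", with a mixed model like that for the primary outcome, "adjusting for multiple comparisons using the Šidák method to maintain the overall confidence at 95" per cent.
- **Aim 2 (Data Analysis for Aim 2).** "Since there will be a number of secondary outcomes, we will use the Šidák method". The section opens with "Secondary measures of self-efficacy, pain coping, patient activation, social support, and health-related quality of life are continuous measures", and later adds utilization counts: "number of ED visits, hospitalizations, outpatient visits, telephone visits, and analgesic prescriptions, including opioids".

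Neither place says single-step or step-down, or how many tests form the family. On timing, the data collection section says "Assessments will be given at baseline, 6 and 9 months", so each scale could contribute one or two tests. The sample size paragraph ("With a two-sided test and a Type I error of .05") concerns the primary BPI total score only and claims no power for any secondary outcome.

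**The concern.** Single-step Šidák compares every p-value in a family of K with the same threshold, however many of the others have already been rejected. The step-down version orders the p-values, tests the smallest at that threshold, and relaxes the threshold after each rejection. It holds the familywise error rate at the same level under the same independence or positive-dependence condition.

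Aim 2 asks which of several outcomes peer coaching changes, in a trial sized for the primary outcome alone. If coaching truly affects two or more of them, a fixed threshold gives up power that could be kept at no cost in familywise error. If the sponsor already means step-down, the text still needs the word, because the two versions can give different verdicts on the same data.

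**Working it through.** **Inputs from the documents.** Familywise level .05, from the 95% overall confidence stated for the subscales; taken to apply to Aim 2 as well. Two BPI subscales. Five continuous Aim 2 constructs.

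**Assumptions (not in the documents).** K = 5 for Aim 2 and K = 2 for the subscales, one time point each. Each truly affected outcome has 80% power at unadjusted two-sided .05, so its z-statistic has mean 1.960 + 0.842 = 2.802. A lower value, 50% (mean 1.960), is also shown. Equal correlation between outcomes, 0 to .5 unless stated.

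**1. The plan's 95% target reproduces.** The single-step threshold is 1 − .95^(1/K).
- K = 2: .02532, and (1 − .02532)² = .95.
- K = 5: .01021, and (1 − .01021)⁵ = .95.

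Single-step Šidák therefore meets the target exactly under independence.

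**2. Thresholds.** Step-down compares the i-th smallest p-value with 1 − .95^(1/(K−i+1)) and stops at the first failure.

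| K | Single-step | Step-down, in order |
|---|---|---|
| 2 | .0253 for both | .0253, .05 |
| 5 | .0102 for all | .0102, .0127, .0170, .0253, .05 |

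The first threshold is the same and each later one is larger, so no single-step rejection can be lost. None was lost in simulation.

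**3. Single-step power by formula.** With two-sided critical value c, power is approximately Φ(mean − c).
- K = 5, c = 2.569: Φ(2.802 − 2.569) = Φ(0.233) = 59%.
- K = 2, c = 2.236: Φ(2.802 − 2.236) = Φ(0.566) = 71%.
- K = 5 at 50% unadjusted power: Φ(1.960 − 2.569) = Φ(−0.609) = 27%.

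**4. Step-down power by simulation** (at least 100,000 families per cell).

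| Family | Truly affected | Unadjusted power | Single-step | Step-down |
|---|---|---|---|---|
| 5 | all 5 | 80% | 59% | 69–71% |
| 5 | 3 | 80% | 59% | 63% |
| 5 | 1 | 80% | 59% | 59% |
| 5 | all 5 | 50% (correlation .4) | 27% | 33% |
| 2 | both | 80% | 71% | about 77% |

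Entries are average power per truly affected outcome.

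**5. What does not change.** Both versions test the smallest p-value at the same threshold, so the chance of at least one rejection is identical. With all five real at correlation .5 it is 89.4% for both. With no real effects, K = 5, familywise error is 5.0% for both at correlation 0 and about 4.3% for both at .5. With three of five real, step-down uses more of the allowance (about .034 against .019) but stays below .05.

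**The case against.** The strongest reply is that nothing here is wrong. Single-step Šidák is a valid method that meets its stated target, and no power for Aim 2 was promised. That stands. A reader might infer that the plan contains an error or loses a stated power; the documents support neither.

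Second, the wording of the subscale sentence suits single-step, which gives simultaneous 95% intervals directly. Step-down has no equally simple intervals. This stands and is the real trade-off. With K = 5, a second-smallest p-value of .012 would be rejected by step-down (threshold .0127), while its single-step interval would include zero (threshold .0102).

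Third, single-step is an inference from an unqualified name. It is the usual reading, but the documents do not state it.

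Fourth, the gain of 10 to 12 points is the favourable case. It shrinks with weaker effects or fewer real ones: at correlation .4, about 2 points if all five are real at 30% unadjusted power, and under 2 points if two of five are real at 80%. This too stands.

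Two stronger readings fail. One is that single-step is uniformly less powerful. It is only never more powerful, since the two agree on whether anything is rejected and nearly coincide when one outcome is real. The other is that correlated outcomes are where step-down gains most. With all five real at 80% unadjusted power, the gain falls from 11.4 to 10.1 to 9.0 points as correlation goes from 0 to .4 to .7. The gain comes from several effects being real.

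**Conclusion.** This is a cheap improvement for secondary outcomes, not a correction. At familywise .05, step-down Šidák is never less powerful than single-step, and is more powerful when two or more outcomes are truly affected. In a family of five the average gain runs from nothing (one real outcome) through about 4 points (three real) to 10–12 points (all real), at an assumed 80% unadjusted power. It is about 6 points if all five are real at 50%, and 5 to 6 points for the two subscales if both are real. The ordering of the two methods needs only the thresholds. The sizes rest on the assumed power, correlation and family size, none of which the documents give for these outcomes.

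The family matters more than the version. The single-step threshold runs from .0253 for two tests to .0026 for twenty, and neither version can be applied until the tests are counted.

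**What to change.** In both places under Data Analysis (the BPI subscales and Aim 2):

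- Specify step-down (Holm-)Šidák at familywise .05 for the hypothesis tests.
- List each family: which outcomes and SF-36 scores, 6 months only or 6 and 9 months, and whether the utilization counts are included. Hospitalizations appear in the Aim 2 analysis list but not in the Aim 2 measures section; reconcile the two before counting.
- Keep single-step Šidák for any simultaneous 95% intervals, and state in the report that a step-down rejection may occasionally appear beside an interval that includes zero.

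The cost is a few lines of text, with no new data, participants or models. Make the change before outcomes are compared by arm, since choosing the version afterwards would undermine the familywise guarantee. If the sponsor prefers tests and intervals that always agree, staying with single-step is defensible; the plan should then say so and still list the family.

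### Utilization counts: with a coach effect in one arm only, the treatment coefficient is a median-coach rate ratio, and read as a ratio of mean counts it leans towards coaching lowering use

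*Combined protocol and SAP*

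**What the plan says.** The Data Analysis for Aim 2 section says that utilization over nine months will be "analyzed using a generalized linear mixed model, assuming the counts follow a Poisson or negative binomial distribution". On the model terms it says "Explanatory variables in the model will include treatment indicator and, if necessary, a random effect for peer coach within the treatment group only", and it adds covariates that differ significantly between arms. It also allows for excess zeros: "If counts include a high proportion of zeros, a zero-inflated count model may be required". No link is named. Nothing says whether the reported effect is specific to a coach or a ratio of mean counts, and no Veteran-level random effect is listed for the counts.

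The one-arm coach term comes from the linear model for BPI in the Data Analysis for Aim 1 section: "Random effects will include a random patient-specific intercept and a random effect for peer coach within the treatment arm only". There the coach effect is normal with mean zero.

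For the other secondary scales the Aim 2 section has a fallback: "If a linear mixed model does not seem appropriate for a given scale, then a generalized linear mixed-effects model will be used". It names neither a distribution nor a link.

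**The concern.** In a linear model, a mean-zero coach effect in one arm leaves that arm's mean unchanged, so the treatment contrast keeps its meaning. On a log scale it does not. Exponentiating a mean-zero normal effect gives a mean above 1, so the coached arm's mean count exceeds exp(b0 + b1). The control arm has no matching term to cancel this. The fitted coefficient and the ratio of mean counts then differ whenever coaches vary, and always in the same direction.

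The outcomes include ED visits, outpatient visits and opioid prescriptions, where most readers want to know whether mean use changed. If exp(b1) is reported without comment, the trial could present coaching as reducing use when mean use is the same in both arms.

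**Working it through.** **Inputs from the documents.** The Sample Size Determination section gives 102 coached and 80 control Veterans before attrition, with 3 Veterans per coach. With 15% attrition, 102/.85 = 120 and 80/.85 = 94.1, taken as 95; 120/3 = 40 coaches. These reproduce the plan's enrolment figures. The plan states no design figure for the utilization models, so there is nothing further to reproduce.

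**Assumptions.** A log link; a coach effect u ~ N(0, s2), carried over from the Aim 1 model; and s2 over a range, because none is given for counts. The ICC of .3 in the sample-size section is for BPI and cannot be converted to s2.

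**Algebra.**
- Control mean: exp(b0).
- Coached mean: exp(b0 + b1) × E[exp(u)] = exp(b0 + b1 + s2/2).
- Ratio of mean counts: exp(b1 + s2/2).
- Hence exp(b1) = ratio of mean counts × exp(-s2/2).

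If mean use is equal, b1 = -s2/2, not 0:

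| s2 (assumed) | exp(-s2/2) |
|---|---|
| .05 | 0.975 |
| .10 | 0.951 |
| .25 | 0.882 |
| .30 | 0.861 |
| .50 | 0.779 |

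**Simulation, negative binomial.** Equal true means, 40 coaches × 3 against 95 controls, assumed mean 6 and dispersion 0.5, coach term always fitted, Wald test at .05, 400 runs per row. Nominal rejection is 2.5% in each direction.

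| s2 | exp(b1) | Rejects, lower use | Rejects, higher use | exp(b1 + s2/2) |
|---|---|---|---|---|
| 0 | 0.99 | 3.3% | 2.2% | 1.00 |
| .10 | 0.96 | 5.5% | 1.8% | 1.00 |
| .25 | 0.89 | 12.5% | 0.7% | 1.00 |
| .50 | 0.79 | 33.0% | 0.3% | 0.99 |

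The raw ratio of arm means was 0.99–1.00 throughout. With mean 1 and s2 = .25, exp(b1) was 0.90, with 7.7% of runs rejecting towards lower use and 1.0% towards higher. With mean 8 and dispersion .7, exp(b1) was 0.95 at s2 = .1 and 0.86 at s2 = .3, with total rejection of 8.3% and 17.2%.

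**Simulation, Poisson, no coach effect at all.** With overdispersed counts (mean 6, dispersion 0.5), exp(b1) was 0.92 and 22.8% of runs rejected towards lower use. The coach term, the only place for extra variation, took an estimated variance of 0.161 in the coached arm, and exp(-0.161/2) = 0.923 accounts for the shifted estimate. The rejection rate has a second cause: Poisson standard errors are too small for overdispersed counts.

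**The case against.** Several points on the other side stand.

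- **The estimand is not stated.** The plan never says that exp(b1) will be reported as a ratio of mean counts, and exp(b1) is a valid contrast for a median coach. A reader might infer that the model is simply wrong; the documents do not support that. The fault is that nothing stops the coefficient being read or tested as a ratio of means.
- **The coach term is conditional.** Without it there is no shift of this kind. Taking the condition as a 5% boundary likelihood-ratio test (an assumption; mean 8, dispersion .7, 600 runs), the term was kept in 15%, 35% and 85% of runs at s2 = .05, .1 and .3. The rate ratios were 0.98, 0.97 and 0.86, and total rejection was 5.3%, 8.5% and 17%. At s2 = .1, omitting the term altogether gave 7.7%, so little of that excess is due to the shift. At .3 the condition gives almost no protection.
- **Coach variance may be modest.** The Peer Coach-Veteran Sessions section bars coaches from advising on medication, though it also has them refer Veterans to physicians.
- **Poisson may not survive.** Negative binomial is offered and the Aim 1 section promises checks of fit. The high Poisson error rates are therefore not a forecast for this trial.
- **Multiplicity.** With six tests assumed, the Šidák level is 1 - .95^(1/6) = .0085, and rejection at s2 = .3 fell to 4.7%. That is still inflated, and the adjustment does not re-centre the estimate.
- **The direction does not carry over to other links.** On a logit scale it depends on which side of 50% the probability lies, so nothing directional can be said about the fallback for scales.

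**Conclusion.** The concern holds as a should-fix on secondary outcomes. Given a log link and a retained normal coach effect, the factor exp(-s2/2) is exact and below 1 for any s2 above 0. Its size depends on a variance that the documents do not give: about 2–5% at s2 of .05–.10, which is minor, and about 12–14% at .25–.30, which is material and sends nearly all false rejections towards lower use. Plain Poisson with no Veteran-level overdispersion term adds a shift of its own, even when coaches do not differ.

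A reader might go further and infer that the trial will report a spurious reduction in use. The documents do not support that: the coach term may be dropped, s2 may be small, and negative binomial may be chosen. The linear BPI analysis is unaffected.

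**What to change.** Amend the Data Analysis for Aim 2 section as follows.

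1. State the log link and make the ratio of mean counts the reported effect for every utilization outcome.
2. Model overdispersion in both arms: negative binomial, not plain Poisson.
3. Estimate the ratio in one of two ways, chosen in advance: a log-link GEE clustered on coach, with each control a cluster of one and small-sample-corrected robust errors; or the negative binomial mixed model, reporting exp(b1 + s2/2) with a bootstrap interval over coaches.
4. If a zero-inflated model is used, compute the ratio of marginal means from both parts. With structural-zero probability p in each arm, it is [(1 - p coached) × exp(b1 + s2/2)] / (1 - p control), so exp(b1 + s2/2) alone is not enough unless p is the same in both arms.
5. For any scale that falls back to a mixed model with a non-identity link, report the marginal contrast.

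The cost is SAP wording and slightly different code, with no change to recruitment or data. The downside is that robust errors with about 40 coaches need the small-sample correction and may stay slightly above nominal: a coach-clustered marginal ratio gave 3.7% to 8.0% rejection across the mean-8 scenarios, with a Monte Carlo standard error near 8% of sqrt(.08 × .92/400), about 1.4 points. At s2 near .1 the gain is therefore mainly a correctly labelled estimate; at .3 it is also a better error rate.
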